## Study Summary

Title	A Clinic-Based Case Manager Administered Telephone Intervention to Reduce Cardiovascular Disease Risk in Persons Living with HIV
Short Title	SWOBI-CVD
Protocol Number	Pro00085562
Phase	Phase 3
Methodology	Randomized Controlled Trial
Study Duration	24 months
Study Center(s)	Single-center
Objectives	To assess the impact of telephone-based case manager administered interventions in improving ASCVD risk factor outcomes among HIV-infected clinic patients.
Number of Subjects	50
Diagnosis and Main Inclusion Criteria	Patients diagnosed with HIV and either hyperlipidemia or hypertension
Duration of administration	24-weeks
Statistical Methodology	Generalized linear mixed regression models will be used to assess the changes in systolic blood pressure and LDL-c over the period of the intervention, accounting for repeated measurements within subjects as well as clustering of subjects within providers. Bivariable and multivariable analyses will be conducted for all covariates. To test for the effect of time on the differences in SBP and LDL-c between the groups, we will fit a constrained longitudinal data model (cLDA).  We will fit models with time as a categorical variable (based on the time of outcome measure collection) and as a continuous variable, to determine the best model fit.

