##### **4.4.1 Reasons for withdrawal:**

The voluntary nature of studies allows for participants to withdraw from the study at any point for any reason. Subjects may be withdrawn from the study if a serious adverse event (SAE) occurs. Subjects may be withdrawn if:

1. They withdraw their consent
2. In the opinion of the investigator, continuation of study participation would be hazardous to the participant, or compromise study findings.

The reason for any subject's discontinuation and the date of withdrawal will be recorded in the subject's case file. The subject's case file, which will be completed up to the point of withdrawal will be retained for six years. The study report will include reasons for subjects' withdrawals as

well as details relevant to the subjects' withdrawals. Any subject withdrawn from the trial prior to completion will undergo all procedures indicated in this protocol as being scheduled to occur at discharge or upon early withdrawal. Any subject withdrawn due to an adverse event (whether serious or non-serious) or any clinically significant abnormal laboratory test value will be evaluated by the principal investigator, and will be treated and followed up until the symptoms or values return to normal or acceptable levels, as judged by the Principal Investigator. Relevant post-study procedures will be performed, wherever possible, on subjects who elect to withdraw.

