## **5.7 Control group**

Participants assigned to the control group will receive usual clinical care enhanced with a series of 12 packets of educational handouts delivered to patients every two weeks for 24 weeks. . Educational pamphlets will be delivered on one of six topics on a rotational basis (two rotations over a 6-month study period). The topics to be covered by the educational material are as follows: CVD Knowledge and Risk Perception, Medication Reconciliation, Dietary Assessment and Education, Physical Activity and Weight Management, Smoking Cessation, Stress Management. On enrollment, participants will determine the optimal mode of delivery for the educational material (email, regular mail, or text). All participants in the control and intervention arm will complete the following study assessments: 1) in-office BP obtained by a trained research assistant (0, 6, 12, 18 months) 2) lipid profile (0, 6, 12, 18 months)(the default will be to collect data from lipid profiles done as part of routine clinical care, within 4 weeks of baseline visit; if lipid information is not available or exceeds acceptable time point, lipid panel will be collected by the research staff). 3) 10-year ASCVD risk score (0, 6, 12, 18 months) 4) provider trust and communication survey (0, 6, 12, 18 months).

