first module, the social worker will make a secondary assessment of the participant's health literacy level. The social worker will have the final decision as to which version of the module the participants will receive. During the call, the social worker will follow the prompts of a telephone script. As part of the intervention, the SW will incorporate MI techniques at different times during the phone call based on the direction of the conversation. Towards the end of each call, the participant will have the option to review any or all of the corresponding educational materials relevant to the module. Each of these calls will take between 30-45 minutes to administer. At the conclusion of the study telephone visit, participants will be delivered a package of educational pamphlets similar to those administered to participants in the control arm. Like the control arm, a total of 12 packets will be delivered to intervention participants via their method of choice. Since this pilot study seeks to determine the independent effect of the SW-based intervention, SWs will be instructed not to feedback on study-related telephone interactions to the participant's provider. This will be facilitated by the physical separation between the SW offices and the provider work area. Recruitment efforts will also be tailored to inform providers about the study with the minimal amount of details on the intervention available to avoid undue influence on their practice patterns.

All study follow up visits will be conducted within a +/- 21 day window.

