#### **5.10 Post study intervention**

Participants will be followed after the 24-week intervention at 48 (6-month post intervention) and 72 weeks (1 year post intervention) to assess the durability of the intervention's impact. At those visits, we will collect blood pressures, anthropomorphic and lipid panels similar to the first two study visits. We will also conduct patient-reported data on the durability of the intervention using formal assessment tools for heart-healthy behaviors at each visit.

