## Statistical Plan

### **6.1 Sample size Determination:**

Given that this is a pilot study, our goal is to determine the effect size of the intervention to determine the statistical power needed for subsequent larger studies. Based on our assessment of the recruitment pool and resources available through the award, we will enroll 25 patients in each arm ( $n = 50$ ) with anticipated 20% dropout rate over 6 months for an estimated final analysis sample of 40 patients. Based on previous studies, we can anticipate a mean systolic blood pressure change of 7.6 mmHg, and a standard deviation of 15 mm Hg, for an effect size of 0.51. An effect size of  $< 0.3$  will be considered insignificant.

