### **6.2 Statistical Methods**

Data on the outcome variables (blood pressure, non-HDL/LDL, 10-year ASCVD risk score) for each arm will be collected at weeks 0, 6, 12 and 18 months. Summary statistics of the study cohort will be reported for every interim timepoint. Generalized linear mixed regression models will be used to assess the changes in systolic blood pressure and LDL-c over the period of the intervention. Models will be fit with an interaction term to account for the difference of differences (DID) at each timepoint in the study (on intervention and post intervention timepoints to assess durability of the intervention's effect) to assess the treatment effect between the two arms. The p-value of the interaction term will serve as significance testing for the difference between the outcome value difference of the two study arms. The same technique will be used for the secondary analysis of ASCVD risk scores.

Missing data will be handled as follows:

- Variables with more than 30% missingness will be dropped from the analysis regardless of reason
- Variables with less than 30% missingness will be evaluated by individual observations. If the data point is determined to be missing at random, then values will be imputed in its place using multiple dataset imputation methods. If the data point is determined to be not missing at random, then the observation of missingness will be reported in the summative reporting after the reasons for the patterns of missingness have been determined. The missing values will then be imputed by the predicted linear regression model.
- Any observations without data from the intervention completion (week 24) timepoint will be excluded from the analysis

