### **6.3 Subject Population(s) for Analysis**

All randomized subjects with at least partial outcome data for the baseline and week 24 timepoints will be included in the analysis, regardless of missingness of the post-intervention timepoints.

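### The only analysis set drops every randomised participant with no week-24 outcome data, so no all-randomised comparison is planned

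*Combined protocol and SAP*

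**What the plan says.** The third missing-data bullet of section 6.2 reads: "Any observations without data from the intervention completion (week 24) timepoint will be excluded from the analysis". Taken alone, an observation could mean a data row. Section 6.3 settles that it means a person: "All randomized subjects with at least partial outcome data for the baseline and week 24 timepoints will be included in the analysis". It adds that gaps at the post-intervention visits do not matter. So a missed later visit is tolerated, but having no week-24 outcome data removes the participant. Someone with some week-24 outcomes stays in.

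Section 6.1 is consistent with this. It enrols 25 per arm "with anticipated 20% dropout rate over 6 months for an estimated final analysis sample of 40 patients".

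The models in section 6.2 test an arm-by-time interaction (a difference-in-differences, DID) at each timepoint, both during and after the intervention, and use the same technique for the ASCVD risk score. The Study Summary also commits to a cLDA but attaches no population to it. No intention-to-treat set, all-randomised analysis or sensitivity analysis appears anywhere.

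The data collection is wider than the analysis set:
- Section 5.7 schedules blood pressure, lipids and risk score at 0, 6, 12 and 18 months in both arms: "All participants in the control and intervention arm will complete the following study assessments".
- Section 5.10 adds follow-up at 48 and 72 weeks.
- Section 4.4.1 provides for early withdrawal: "Any subject withdrawn from the trial prior to completion will undergo all procedures indicated in this protocol" for discharge or early withdrawal.
- Section 5.8 sets the visit window: "All study follow up visits will be conducted within a +/- 21 day window".

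**The concern.** Randomisation protects a comparison of everyone randomised. Here membership of the analysis set is decided up to 24 weeks later, in a behavioural trial where only one arm receives 12 telephone calls of 30 to 45 minutes, so attendance could plausibly differ by arm. Section 6.1 says the pilot's purpose is to obtain an effect size for planning larger studies. As written, that figure describes only people who supplied week-24 data, at every timepoint, and a reader would have no all-randomised result with which to judge whether the exclusion mattered.

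Two further consequences follow. Readings that the protocol sets out to collect are thrown away. And the size of the analysis set is not fixed in advance, because the plan does not say whether an early-withdrawal reading, or one outside the 21-day window, counts as week 24.

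The second bullet of section 6.2 (imputation) does not rescue these participants: section 6.3 and the planned 40 indicate that the exclusion takes precedence. That this precedence is unwritten is only a wording gap.

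**Working it through.** **Inputs from the documents.** 50 randomised, 25 per arm; 20% dropout; 40 analysed; SD 15 mmHg; four outcome visits.

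**Inputs assumed.** Correlation between visits (rho) 0.4 to 0.6; odds ratio (OR) for dropout per SD of baseline SBP 1.25 to 3; dropout 20%/20% or 30%/10% by arm (intervention/control); 0 to 6 people who miss only week 24 and return.

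**1. The plan's own figure.** 50 x (1 - 0.20) = 40, as stated.

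**2. How many are excluded.** 50 x 0.20 = 10 expected; the central 95% of Binomial(50, 0.2) is 5 to 16. If none, half or all of those 10 give an early-withdrawal reading that counts as week 24, the exclusions are 10, 5 or 0.

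**3. What is discarded, per outcome.** About 10 baseline readings, plus 2 later visits x 0 to 6 returners = 0 to 12 later readings.

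**4. Conditional bias of the completer DID, with no true effect.** Dropout was simulated as a logistic function of standardised baseline SBP, with 2,000,000 draws per arm. If selection shifts one arm's completer baseline mean by m, its week-24 mean shifts by rho x m, so the DID is off by (1 - rho) x m in absolute size. For example, m = 2.77 mmHg at OR 3 and 20% dropout gives 0.6 x 2.77 = 1.66 at rho 0.4. Results in mmHg, with the mechanism in the intervention arm only, for rho 0.4 / 0.5 / 0.6:

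| OR | Dropout 20%/20% | Dropout 30%/10% |
|---|---|---|
| 1.25 | 0.39 / 0.32 / 0.26 | 0.58 / 0.49 / 0.39 |
| 1.5 | 0.70 / 0.58 / 0.46 | 1.04 / 0.87 / 0.69 |
| 2 | 1.15 / 0.95 / 0.76 | 1.70 / 1.41 / 1.13 |
| 3 | 1.66 / 1.38 / 1.11 | 2.42 / 2.01 / 1.61 |

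With the same OR in both arms the bias is 0 (within 0.02) at 20%/20%, and 0.25 to 1.54 at 30%/10%.

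Across all 48 scenarios (4 ORs x 3 correlations x 4 dropout patterns), the largest absolute bias is 0.016 mmHg if the arm-by-time model is fitted by maximum likelihood with dropouts' baselines kept. It is also 0.016 mmHg if completers are analysed with baseline adjustment.

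**5. Bias against the standard error (SE).** At rho 0.5 and 20 per arm, the DID SE is 15 x sqrt(2/20) = 4.74, and 2.42 / 4.74 = 0.51. The 2.42 arises at rho 0.4 and 30%/10%, where the matching SE is 15 x sqrt(2 x 0.6) x sqrt(1/17.5 + 1/22.5) = 5.24, giving 0.46. Either way it is about half of one SE at most.

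**6. Precision, rho 0.5, 20 of 25 per arm at week 24.**
- DID in completers: 4.74.
- DID with dropouts' baselines: sqrt(2 x 225 x (0.75/20 + 0.25/25)) = 4.62.
- cLDA: 15 x sqrt(0.75 x 2/20) = 4.11.
- Four-visit cLDA (compound symmetry) with 0 / 1 / 2 / 3 returners per arm: week 24 SE 4.11 / 4.09 / 4.08 / 4.06; week 48 SE 4.11 / 4.01 / 3.92 / 3.83. Completers only: 4.11 at both visits.

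**7. Interaction with the first bullet of section 6.2.** That bullet drops any variable with more than 30% missing, which is 16 or more of 50. P(X >= 16) at 20% dropout is 0.031.

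**The case against.** The strongest reply is that the plan already names a model that removes the bias. With baseline and week 24 only, a cLDA in completers is equivalent to a baseline-adjusted comparison, and step 4 shows that this has essentially no bias under the assumed mechanism. The bias needs both the exclusion and the unadjusted DID of section 6.2, and every driver of it is assumed. This stands, and bias is therefore not the ground for the point. It does not supply an all-randomised comparison, and section 6.2 describes its significance test as that of the DID interaction.

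Second, the discarded readings carry little information. Baselines of dropouts do not change the cLDA SE at all when nobody returns, and the documents do not predict returners. Most of the week-24 contrast would still come from the same 40 or so people. This also stands; the gain in precision is small.

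Third, the set does not condition on calls received, so it is a modified intention-to-treat set and not a per-protocol set, and the 40 in section 6.1 is a planning allowance that by itself excludes nobody. Both are fair. If every early-withdrawal reading counted as week 24, the number excluded could even be 0. But the plan does not say so, and leaving that mapping open until data are in hand is part of the problem.

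Fourth, this is a 50-person pilot. Its product is the effect size, so whom that figure describes matters more here, not less.

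**Conclusion.** The concern holds and should be fixed; it is not fatal. The exclusion is explicit in sections 6.2 and 6.3, agrees with section 6.1, and applies to every between-arm comparison. About 10 of 50 are expected to be removed (5 to 16 by chance alone at 20% dropout; fewer if early-withdrawal readings count).

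The conclusion rests on the absence of any all-randomised comparison and on the discarding of data the protocol collects. Neither depends on the assumed correlations or odds ratios. It does not rest on the bias, which is conditional, 0.3 to 2.4 mmHg when the dropout mechanism acts in one arm only, and nil when dropout is alike in both arms. Nor does it rest on precision.

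**What to change.** 1. Delete the third missing-data bullet of section 6.2.
2. In section 6.3, define the primary set as all randomised participants with at least one measurement of the outcome, analysed as assigned.
3. Make the cLDA in the Study Summary the primary analysis, fitted by likelihood to all available visits without imputing outcomes, and state the missing-at-random assumption.
4. State that the 30% rule in the first bullet does not remove an outcome visit from this model.
5. State which visit an early-withdrawal or out-of-window reading is assigned to.
6. Keep the week-24 completer analysis as a sensitivity analysis.

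The cost is SAP wording; no new data are needed. The primary result will then rest on missing at random and will not correct dropout that depends on unobserved outcomes. The gain in precision is small.

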### **6.3 Subject Population(s) for Analysis**

All randomized subjects with at least partial outcome data for the baseline and week 24 timepoints will be included in the analysis, regardless of missingness of the post-intervention timepoints.

## Safety

### **7.1 Potential Risks**

### *Loss of confidentiality*

The risks associated with potential loss of confidentiality are low. The staff obtaining data will be properly trained and supervised. Participant data, including audio recordings, will be stored in files on the Duke Division of Infectious Diseases private server, managed by the Duke Office of Information Technology.

### *Detection of clinically significant problems*

Although not caused by study participation, it is possible that clinically significant problems will be detected by study staff. Subjects entering the study will have a history of hypertension or hyperlipidemia so abnormal systolic, diastolic and lipid values are expected. All values that reach a safety threshold (<90 or >180 systolic BP, or <40 or >110 diastolic BP) will be reported to the subjects' care provider immediately (See Section on Adverse Event Reporting).

### *Physical activity*

During the course of the study, SWs may encourage participants to increase their physical activity, increasing the possibility of musculoskeletal injury or unmasking of ischemic heart disease. Risks from increased physical activity will be minimized by encouraging moderate rather than vigorous activity. Providers will respond to these patient problems per usual medical care.

### *Smoking*

Smoking participants will be encouraged to quit smoking, increasing the possibility of withdrawal symptoms from nicotine dependence.

### *Psychological risks*

For the purpose of the study assessments, participants will be asked about personal characteristics such as race/ethnicity, and socioeconomic status that may be uncomfortable to answer. Only questions that are important to inform the study outcomes will be asked during the course of the trial. Participants will be informed that they may refuse to answer any questions, and continue to participate in the study. It is also possible that participants may be uncomfortable talking to the SW about some topics that will be discussed as part of the intervention.

## **7.2 Protection against risks**

### *Protection of participants' confidentiality*

Since this study involves people with HIV, steps will be taken to protect patient data and identities. All research staff will be trained in initial, follow up and monitoring training specific to the trial in addition to the Research Ethics and Compliance training via Collaborative Institutional Training Initiative (CITI), which will ensure the understanding of all the ethical issues involved in research. All consent forms signed by the participants will be maintained in locked files with limited access, separate from any subject data and will only be accessible to the study team. Any personal identifiers linked to the data will be replaced with subject IDs in all patient records. Participants will be made aware of these risks at the time of informed consent, prior to study participation.

### *Blood Pressure*

The participants will have a high risk for CVD and thus many will be prescribed hypertension medications by their health care provider at the outset of the study. It is likely that as a result of increased monitoring, we will detect more episodes of abnormal BP values. BP will be measured at each follow up visit. Participants will have access to their regular providers as well as the study investigator designated as the clinical contact for the study: [name] (infectious disease physician; Duke Health). An average SBP at any study visit  $>180$  mm Hg and/or diastolic is  $>110$  mm Hg will be considered an alert value and will trigger assessment by the study clinician. Additionally, an average BP at any study visit that is  $<90$  systolic or  $<40$  diastolic would also be considered an alert value and would trigger an assessment by the study clinician.

Participants who have an alert BP reading during study visits will be directly assessed for cardiovascular symptoms during the visit. Once an alert value has been confirmed, the participant will be triaged according to follow-up recommendations from Joint National Committee Recommendations (JNC 8). If at any time, participants have symptoms of acute end organ damage (i.e. current chest pain, dyspnea at rest, new onset of blurry vision, or new neurological deficits consistent with a stroke) in the context of an elevated BP measurement (SBP  $>180$ , and/or DBP  $>110$ ), participants will be asked to contact the clinician and will be advised and assisted in seeking emergency medical care.

For participants in the intervention group whose average SBP  $>180$  and DBP  $>110$  or SBP  $<90$  or DBP  $<40$  but are without acute symptoms, the participant's primary provider will be notified. Follow up contact with the study staff will occur within one week. All abnormal blood pressure results will be communicated to the clinic director at each site who will be an integral part of triage and ensuring follow up. The SW will then generate a note to be entered into the electronic medical record and will communicate directly with the subject's PCP.

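### The one-week staff follow-up after a symptom-free blood pressure alert is written for the intervention arm only; it should cover both arms

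*Combined protocol and SAP*

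**What the plan says.** The alert rules are in section 7.2 (Blood Pressure), with a related rule in section 7.1 (Detection of clinically significant problems).

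**Rules with no arm limit.** Section 7.1 has every reading beyond a safety threshold (systolic below 90 or above 180, diastolic below 40 or above 110) reported at once to the subject's care provider. Section 7.2 has the study clinician assess any alert value. It continues: "Participants who have an alert BP reading during study visits will be directly assessed for cardiovascular symptoms during the visit". Confirmed alerts are triaged by JNC 8 recommendations, and symptomatic participants are helped to emergency care.

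**The paragraph on alerts without acute symptoms.** It begins "For participants in the intervention group whose average SBP", sets the thresholds, and has the primary provider notified. Then come three sentences, in this order:

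- First, on contact after the visit: "Follow up contact with the study staff will occur within one week".
- Second, on reporting within the clinic: "All abnormal blood pressure results will be communicated to the clinic director at each site", with that director given a part in triage and follow-up.
- Third, on the SW's part: "The SW will then generate a note to be entered into the electronic medical record and will communicate directly with the" subject's PCP.

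Section 5.7 gives controls usual care plus educational packets and describes no alert pathway. Section 5.8 states an aim that bears on this: "Since this pilot study seeks to determine the independent effect of the SW-based intervention". For that reason, "SWs will be instructed not to feedback on study-related telephone interactions to the" participant's provider.

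**The concern.** Two participants with the same extreme, symptom-free reading should have the same written follow-up, whatever their allocation. As drafted, one has a dated contact from study staff and the other does not. The plan gives no reason for the difference.

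A second, weaker issue is comparability. Systolic blood pressure is in the primary objective (section 2.1), and section 6.2 tests the difference between arms during and after the intervention. Extra blood pressure follow-up in one arm is a co-intervention outside the telephone programme that section 5.8 tries to isolate. If the SW's note and PCP contact are also confined to that arm, they could show the treating clinician which arm the patient is in. Because low readings also trigger the paragraph, any change in treatment could go either way.

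**Working it through.** No figure in the plan needs reproducing. The check sets the provisions side by side, then asks which comparisons they could touch.

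**Step 1. Each step after a symptom-free alert, by arm.**

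| Step | Where | Intervention | Control |
|---|---|---|---|
| Immediate report to care provider | 7.1 | yes | yes |
| Study-clinician assessment | 7.2 | yes | yes |
| Symptom check at the visit | 7.2 | yes | yes |
| JNC 8 triage of a confirmed alert | 7.2 | yes | yes |
| Primary provider notified | 7.2, last paragraph | yes | not here, but covered by 7.1 |
| Study-staff contact within one week | 7.2, last paragraph | yes | not written |
| Clinic director told; role in follow-up | 7.2, last paragraph | yes | yes, on a plain reading |
| SW note in the medical record | 7.2, last paragraph | yes | unclear |
| SW contact with the PCP | 7.2, last paragraph | yes | unclear |

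**Step 2. How far the arm limit reaches.** Only the first sentence of the paragraph names an arm. The one-week contact follows directly from it and precedes the sentence on all abnormal results, so it stays tied to the intervention group. The SW sentence comes after that wider sentence and speaks of the subject, not of an arm. The Medication adverse effects text in section 7.2 also has the SW counsel each participant, so the SW's role towards controls is not drafted consistently. Both readings of the SW sentence are open:

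- Intervention arm only: that arm has an additional provider contact.
- Both arms: the SW enters the care of controls, for whom section 5.7 describes no SW role.

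**Step 3. Which contrasts could be touched.** Sections 3.1 and 5.10 place blood pressure visits at weeks 0, 24, 48 and 72. An alert at visit *v* can influence a contrast at visit *c* only if *v* < *c*:

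- Week 24: alerts at {0}, one visit.
- Week 48: alerts at {0, 24}, two visits.
- Week 72: alerts at {0, 24, 48}, three visits.

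So only a baseline alert can feed the 24-week contrast; later alerts bear on durability alone. Section 4.3 plans the baseline visit alongside a clinical visit with an HIV provider, which leaves even less for an added contact to change.

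**Step 4. Can an effect be sized?** It would take the number of intervention participants with an earlier alert and the systolic change due to the extra contact, beyond provider reporting, clinician assessment and triage. The documents give neither, so no mmHg figure is offered. The triggers are extreme values, and the high trigger in this paragraph joins the systolic and diastolic limits with *and*, where the alert definition above it uses *and/or*. Read literally, that makes it rarer still.

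**The case against.** The strongest reply is that this is a drafting slip with little behind it. The paragraph refers to a director at each site although the Study Summary describes a single-center trial. Its high trigger does not match the alert definition above it, and no rationale for treating the arms differently appears anywhere. Controls also have follow-up in substance, through triage, provider reporting and the clinic director. All of that stands, and it is why the point is minor. It does not supply the missing one-week contact: staff following the text would make that contact for one arm only.

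A reader might infer three stronger things that the documents do not support:

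- **That controls with an alert get no safety response, or that their provider is not told.** Section 7.1 and the earlier paragraphs of section 7.2 cover all subjects.
- **That the SW's contact with the PCP breaks the no-feedback rule.** Section 5.8 limits that rule to telephone interactions, whereas these alerts arise from readings at study visits. The most one can say is that an SW contact confined to one arm would sit awkwardly with the aim of isolating the SW effect.
- **That the systolic contrast is materially biased.** That needs an alert rate and an effect of the added contact, neither of which is given. Timing and the protections already in both arms point to very little.

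It can also be said that replacing the SW goes further than the asymmetry requires. That is fair; it is offered below as a preference.

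**Conclusion.** The point holds in a limited form. The one-week study-staff follow-up after a symptom-free alert is written for the intervention group and nowhere else. The SW note and PCP contact may cover one arm or both, and the text does not settle which. What controls lack in writing is a dated contact by study staff.

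This is a minor matter of participant safety and equal handling of the arms. Any effect on systolic blood pressure is probably negligible and cannot be quantified from the documents. The conclusion rests on reading the opening words of the paragraph as governing the one-week sentence, and on reading the clinic-director sentence as covering all participants, as its wording suggests. If the first assumption is wrong, only a clarification is needed, and the same edit provides it.

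**What to change.** Replace the opening of the paragraph with *For participants in either arm*, so that provider notification, the one-week contact, the medical-record note and the PCP contact apply to everyone.

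Preferably, also have the study clinician or coordinator write the note and contact the PCP, by the same route in both arms, in place of the interventionist SW. This settles the ambiguity about the SW's role with controls and keeps the author of the note from revealing the allocation. An SW who learns of a safety problem during a call would still report it to the coordinator and principal investigator under section 5.9.

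The cost is wording in one paragraph and a few extra notes and contacts, as planned coverage goes from 25 to 50 participants. No safety cover is lost, because the steps common to both arms stay in place.
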